## **5.2. Primary efficacy analysis**

The primary efficacy endpoint is the qualitative measurement of the viral activity parameter hepatitis B surface antigen (HBsAg) determined using standard serologic assays in a central laboratory.

Descriptive statistics (specified in section 2.6) and the comparison of the efficacy of 24 weeks treatment (i.e. combinations of JNJ-56136379 monotherapy, JNJ-56136379+NA and placebo+NA) is mainly of interest. These comparisons will be done overall, by subject population (i.e., subjects currently not being treated or virologically suppressed by current NA treatment), and by HBeAg status (Positive or Negative).

### **5.2.1 Analysis of the primary endpoint**

The following tabulation will be included:

- Descriptive statistics of the actual values (original unit and log10 transformed values) and the change from baseline (log10 transformed values) over time according to the specification described in section 2.6 will be included.
- Least Square (LS) means (SE) of change from baseline (and 95% confidence interval) per time point and overall based on log10 transformed values will be analyzed by subject population and part using mixed effects model for repeated measures. Also P-values for treatment, time, their interaction and overall will be added.
- LS means (SE) of change from baseline (and 95% confidence interval) per time point and overall based on log10 transformed values will be analyzed by subject population, part and by HBeAg status using mixed effects model for repeated measures. Also, P-values for treatment, time, their interaction and overall will be added.

---

### 5.2.1.1 Mixed effects model for repeated measures

The main comparisons of interest in the efficacy analyses are:

- to evaluate the efficacy of 24 weeks of JNJ-56136379 monotherapy versus placebo+NA;
- to evaluate the efficacy of 24 weeks of JNJ-56136379+NA versus placebo+NA;
- to evaluate the efficacy of 24 weeks of JNJ-56136379 monotherapy versus JNJ-56136379+NA.

The primary endpoint, Week 24 HBsAg change from baseline, will be analyzed by a comparison of each dose of JNJ-56136379 added to the background NA therapy with the concurrent control arm (placebo + NA), within each of the 4 categories defined by subject population and HBeAg status:

- Low dose (75 mg) of JNJ-56136379+NA with placebo+NA (Part A) in currently not treated HBeAg positive subjects
- Low dose (75 mg) of JNJ-56136379+NA with placebo+NA (Part A) in currently not treated HBeAg negative subjects
- Low dose (75 mg) of JNJ-56136379+NA with placebo+NA (Part A) in virologically suppressed HBeAg positive subjects
- Low dose (75 mg) of JNJ-56136379+NA with placebo+NA (Part A) in virologically suppressed HBeAg negative subjects
- High dose (TBD) of JNJ-56136379+NA with placebo+NA (Part B) in currently not treated HBeAg positive subjects
- High dose (TBD) of JNJ-56136379+NA with placebo+NA (Part B) in currently not treated HBeAg negative subjects
- High (TBD) of JNJ-56136379+NA with placebo+NA (Part B) in virologically suppressed HBeAg positive subjects

---

- High (TBD) of JNJ-56136379+NA with placebo+NA (Part B) in virologically suppressed HBeAg negative subjects

The same comparisons versus placebo+NA as above will also be conducted with JNJ-56136379 monotherapy.

Change from baseline based on log10 transform for quantitative HBsAg, will be analyzed by subject population using mixed effects model for repeated measures [MMRM]) including treatment group, analysis time point (treated as discrete/categorical), their interaction, HBeAg status (in the pooled analysis only), as fixed effects. The covariance structure will include a random intercept at the level of the subject to capture between-subject variability, while within-subject variability will be captured with an unstructured (type=UN) covariance matrix. In case the latter leads to convergence issues, alternative within-subject covariance structures will be considered, in the following hierarchy:

- i) First-order ante-dependence structure (type=ANTE(1)),
- ii) Heterogeneous first-order autoregressive structure (type=ARH(1))
- iii) First-order autoregressive structure (type=AR(1)).

The mean difference, SE adjusted means, p-values and 95% confidence interval (CI) will be constructed around the difference between the LS means of each JNJ-56136379 (open label), JNJ-56136379+NA and placebo +NA at each time point and each factor where appropriate.

In addition, the effect of the subgroups (by subject population and by HBeAg status) on the efficacy parameters will be explored descriptively. A subgroup analysis by subject population and by HBeAg status will be performed using mixed effects model for repeated measures [MMRM]) including treatment group, analysis time point (treated as discrete/categorical) and their interaction as fixed effects. The covariance structure will include a random intercept at the level of the subject to capture between-subject variability, while within-subject variability will be captured with an

---

unstructured (type=UN) covariance matrix. In case the latter leads to convergence issues, alternative within-subject covariance structures will be considered, in the following hierarchy:

- i) First-order ante-dependence structure (type=ANTE(1)),
- ii) Heterogeneous first-order autoregressive structure (type=ARH(1))
- iii) First-order autoregressive structure (type=AR(1)).

Subgroup levels may be combined, or subgroups omitted, if not enough data is available within the subgroup levels.

Data will also be presented graphically by treatment group and by subgroups at all different analysis timepoints (X-axis) and by individual subject.

Graphs for the mean (SE) of the transformed log10 values will be also presented by subgroups at all different analysis timepoints.

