A Bayesian analysis will be conducted for Part A and Part B separately to compare the mean HBsAg change from baseline at Week 24 of JNJ-56136379 as monotherapy and in combination with NA versus placebo+NA by HBeAg subgroup. This Bayesian analysis will incorporate historical data for the placebo+NA arm(s) in an informative meta-analytic predictive (MAP) prior with robustness modifier. For the current sample size simulations, historical data comes from an ongoing systematic literature review on HBsAg declines during NA treatment, resulting in 20 studies including around 2,835 subjects. More details on the eventual historical data, including all references to all studies, will be provided in the Modeling and Simulation Report/SAP. The Bayesian equivalent of power, ie, the likelihood that the posterior probability that the mean change from baseline of HBsAg at Week 24 is larger in the JNJ-56136379+NA arm than in the placebo+NA arm is at least 90%, was determined. The results are summarized in [Table 7](#).

It is concluded that, under the assumptions made, the posterior distribution of the estimate of treatment difference between the placebo+NA and JNJ-56136379+NA arm will be precise enough to allow meaningful conclusions. The probability to detect a treatment effect with at least 90% confidence is 0.80 or higher for the HBeAg-negative subgroup in both subjects currently not being treated and virologically suppressed subjects. For the HBeAg-positive subgroup, power is substantially lower which increases the risk of inconclusive results. However, if the interim analysis at Week 12, Week 24 or Week 48 indicates no safety concerns and a potential benefit, a moderate sample size increase for HBeAg-positive subjects to a maximum of 6 subjects on placebo+NA and 18 subjects on JNJ-56136379 monotherapy and JNJ-56136379+NA per study part may be considered. This will increase the probability to detect a treatment effect in these subgroups from 64% or 57% to around 84%.

**Table 7: Bayesian Power Analysis for the Different Prior Treatment and HBeAg Status Subgroups: HBsAg Change From Baseline**

	HBeAg Status	HBsAg ( $\log_{10}$ IU/mL) Change From Baseline		Sample Size (Placebo+NA/JNJ-56136379+NA)	Power a
		Mean $\pm$ SD	Mean $\pm$ SD		
		Placebo+NA	JNJ-56136379+NA		
Currently not being treated	Positive	-0.35 $\pm$ 0.6	-1.35 $\pm$ 2.16	4/12 b	0.64
	Negative	-0.05 $\pm$ 0.4	-1.05 $\pm$ 2.16	6/18 b	0.84

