### **11.3.3. Other Analyses**

Mean changes and maximum mean decrease from baseline in HBsAg, HBeAg, and HBV DNA levels over time will be tabulated by study treatment together with respective SDs. The proportion of subjects with seroclearance and seroconversion of HBsAg and HBeAg will also be tabulated by study treatment. The proportion of subjects with virologic response and the proportion of subjects with virologic or clinical relapse, defined as HBeAg, HBsAg, and/or HBV DNA levels below and above certain thresholds at different time points, respectively, will be categorized as detailed in the SAP, as applicable. Data will also be presented graphically by study phase, study treatment and by individual subject. All individual values will be presented in subject listings.

The least squares (LS) mean change from baseline in serologic parameters and HBV DNA for each study treatment and time point will be estimated with a repeated measurement model (mixed-effects model for repeated measures) including study treatment and time point as fixed effect. The model will allow for unequal variances between study treatments. A 95% confidence interval (CI) will be constructed around the difference between the LS mean of each study treatment. Other methods to evaluate the changes in serologic parameters and HBV DNA may include slope estimation, time-to-event or proportions of subjects who reach a certain level or who exceed a certain reduction.

The proportion of subjects with sustained reduction/suppression and/or sero-clearance, including but not limited to functional and partial cure, will be determined during follow-up. Single and multiple markers such as HBsAg, HBeAg, HBV DNA and ALT levels will be taken into consideration in this analysis.

Other efficacy endpoints, eg, HBV RNA and HBcrAg, will be analyzed descriptively. For continuous variables, descriptive statistics (n, mean, SD, median, minimum, maximum) will be calculated; mean difference and CIs may be calculated where appropriate and, if appropriate, a general linear mixed model will be used to compare the different study treatments. For categorical variables, frequency tables will be presented. Difference in proportions and CIs may be calculated where appropriate.

Analyses, tabulations and visualizations will be done for both treatment and follow-up phases.

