### APPENDIX 3: SAS CODE FOR THE MMRM MODEL

```
proc mixed data=mod01 (where = (paramcd = 'LGHBSAG' ));  
  by hbeagstat;  
  class avisitn trtlon usubjid;  
  model chg = avisitn trtlon trtlon*avisitn / ddfm=kr2;  
  repeated / type=UN subject=usubjid ;  
run;
```

hbeagstat = HBeAg status at baseline

avisitn = analysis visits

trtlon = Treatment groups

usubjid = subject ID

chg = change from baseline

In case the above leads to convergence issues, alternative within-subject covariance structures will be considered, in the following hierarchy:

```
proc mixed data= mod01 maxopt=1000;  
  by hbeagstat;  
  class avisitn trtlon usubjid;  
  model chg= avisitn trtlon trtlon*avisitn /dist=normal link=identity solution ddfm=kr2;  
  random intercept/subject=usubjid v vcorr;  
  random _residual_ /type=ante(1) subject=usubjid g gcorr;  
  covtest 'int' general 1 0 0 0 0 0 0 0 0 0 0 0 0 0 0 0;  
  covtest 'all var equal' general  
    0 1 -1 0 0 0 0 0 0 0 0 0 0 0 0 0,  
    0 0 1 -1 0 0 0 0 0 0 0 0 0 0 0 0,  
    0 0 0 1 -1 0 0 0 0 0 0 0 0 0 0 0,  
    0 0 0 0 1 -1 0 0 0 0 0 0 0 0 0 0,  
    0 0 0 0 0 1 -1 0 0 0 0 0 0 0 0 0,  
    0 0 0 0 0 0 1 -1 0 0 0 0 0 0 0 0,  
    0 0 0 0 0 0 0 1 -1 0 0 0 0 0 0 0;  
  covtest 'all corr equal' general  
    0 0 0 0 0 0 0 0 0 1 -1 0 0 0 0 0,  
    0 0 0 0 0 0 0 0 0 0 1 -1 0 0 0 0,  
    0 0 0 0 0 0 0 0 0 0 0 1 -1 0 0 0,  
    0 0 0 0 0 0 0 0 0 0 0 0 1 -1 0 0,  
    0 0 0 0 0 0 0 0 0 0 0 0 0 1 -1 0,  
    0 0 0 0 0 0 0 0 0 0 0 0 0 0 1 -1;  
  covtest 'all var&corr equal' general  
    0 1 -1 0 0 0 0 0 0 0 0 0 0 0 0 0,  
    0 0 1 -1 0 0 0 0 0 0 0 0 0 0 0 0,  
    0 0 0 1 -1 0 0 0 0 0 0 0 0 0 0 0,  
    0 0 0 0 1 -1 0 0 0 0 0 0 0 0 0 0,  
    0 0 0 0 0 1 -1 0 0 0 0 0 0 0 0 0,  
    0 0 0 0 0 0 1 -1 0 0 0 0 0 0 0 0,
```

---

```

0      0 0 0 0 0 1 -1    0 0 0 0 0 0,
0      0 0 0 0 0 0 0      1 -1 0 0 0 0,
0      0 0 0 0 0 0 0      0 1 -1 0 0 0,
0      0 0 0 0 0 0 0      0 0 1 -1 0 0,
0      0 0 0 0 0 0 0      0 0 0 1 -1 0,
0      0 0 0 0 0 0 0      0 0 0 0 1 -1 0,
0      0 0 0 0 0 0 0      0 0 0 0 0 1 -1;
run;

proc mixed data= mod01 maxopt=1000;
by hbeagstat;
class avisitn trtlon usubjid;
model chg= avisitn trtlon trtlon*avisitn /dist=normal link=identity solution ddfm=kr2;
random intercept/subject=usubjid v vcorr;
random _residual_ /type=arh(1) subject=usubjid g gcorr;
covtest 'int' general 1 0 0 0 0 0 0 0 0;
covtest 'corr' general 0 0 0 0 0 0 0 0 1;
covtest 'all var equal' general
      0      1 -1 0 0 0 0 0 0 ,

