      0      0 1 -1 0 0 0 0 0 ,
      0      0 0 1 -1 0 0 0 0 ,
      0      0 0 0 1 -1 0 0 0 ,
      0      0 0 0 0 1 -1 0 0 ,
      0      0 0 0 0 0 1 -1 0 ,
      0      0 0 0 0 0 0 1 -1 ;
run;

proc mixed data= mod01 maxopt=1000;
by hbeagstat;
class avisitn trtlon usubjid;
model chg= avisitn trtlon trtlon*avisitn /dist=normal link=identity solution ddfm=kr2;
random intercept/subject=usubjid v vcorr;
random _residual_ /type=ar(1) subject=usubjid g gcorr;
output out=overdisp2 pearson=pearson;
covtest 'int' general 1 0 0;
covtest 'ar1' general 0 1 0;
covtest 'int&ar1' general 1 0 0, 0 1 0;
run;

```

For the pool analysis include HBeAg status as fixed effect in the above models

---

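### The SAP's repeated-measures model fits one covariance structure to all arms, although the protocol says variances may differ by treatment; at the planned SDs the Week 24 SE is about 59–67% too large.

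*SAP*

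**What the plan says.** Protocol 11.3.3 describes a "mixed-effects model for repeated measures) including study treatment and time point as fixed effect" for serologic parameters (which include HBsAg) and HBV DNA. It then adds: "The model will allow for unequal variances between study treatments".

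SAP 5.2.1.1 applies a model of this kind to change in log10 HBsAg, "including treatment group, analysis time point (treated as discrete/categorical), their interaction, HBeAg status (in the pooled analysis only), as fixed effects". The HBeAg-specific version is the same without HBeAg status. The covariance is a random subject intercept plus an unstructured within-subject matrix, with ANTE(1), ARH(1) and AR(1) as fallbacks. The text does not let any of these vary by treatment.

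Appendix 3 agrees. The first model has "model chg = avisitn trtlon trtlon*avisitn / ddfm=kr2" and "repeated / type=UN subject=usubjid", with no grouping by treatment, and the three fallback programs have none either. The closing note is "For the pool analysis include HBeAg status as fixed effect in the above models".

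SAP 5.2.1 lists the resulting LS means, SEs, 95% CIs and p-values under the primary endpoint. The Secondary Analysis part of SAP 5.3 reuses the model for the other viral markers.

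Randomisation is stratified by HBeAg status and by HBsAg level at screening (Protocol 5). Baseline log10 HBsAg is derived (SAP 4.2.2), but neither it nor the HBsAg stratum is in the model.

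**The concern.** The protocol commits to a feature of the model that the SAP and its code do not carry over. Table 7 of Protocol 11.2 ("Bayesian Power Analysis for the Different Prior Treatment and HBeAg Status Subgroups: HBsAg Change From Baseline") plans an active-arm SD roughly four to five times the control SD, and control is the smaller arm. A common variance is then dominated by the larger, more variable active arm and is applied to the ten controls, whose own spread is much smaller. The SE for JNJ-56136379+NA versus placebo+NA comes out too large. Intervals are too wide and p-values too high, and a real HBsAg signal could be read as inconclusive.

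The missing HBsAg term is a separate and smaller matter. If baseline level is prognostic, leaving it out may cost some precision.

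**Working it through.** **Inputs.** SDs from Protocol Table 7: placebo+NA 0.6 (untreated, HBeAg-positive) or 0.4 (the other three cells); JNJ-56136379+NA 2.16 (all cells). Arm sizes 10 and 30 (Protocol 3.1). Planned extra decline 1 log10 IU/mL (Protocol 11.2). Single visit, complete data.

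**The plan's own figures.** Table 7 gives power of 0.64, 0.84, 0.57 and 0.89 for cells of 4/12, 6/18, 3/9 and 7/21. A normal approximation with arm-specific SDs and the SAP Table 3 prior gives 0.61, 0.74, 0.54 and 0.79. The protocol simulated from skewed mixtures whose parameters it does not give; the closest assumed mixture gives 0.67, 0.84, 0.56 and 0.86. The stated power is therefore not exactly reproduced, but neither is it shown to be wrong. A single SD of 2.16 for both arms gives only 0.28–0.41, so the sizing relies on the control arm being much less variable.

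**Formulas.** Common-variance SE = sqrt{[((n0−1)s0² + (n1−1)s1²)/(n0+n1−2)] × (1/n0 + 1/n1)}. True SE = sqrt(s0²/n0 + s1²/n1).

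**Whole population, 10/30.**
- SDs 0.4 and 2.16: common = sqrt{[(9×0.16 + 29×4.666)/38] × (1/10 + 1/30)} = sqrt(3.599 × 0.1333) = 0.69; true = sqrt(0.0160 + 0.1555) = 0.41; ratio 1.67.
- SDs 0.6 and 2.16: common = sqrt(3.646 × 0.1333) = 0.70; true = sqrt(0.0360 + 0.1555) = 0.44; ratio 1.59.

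**Interval at 0.4 and 2.16.** Common: 2.024 (38 df) × 0.693 = 1.40. Arm-specific: 2.032 (Satterthwaite, about 34 df) × 0.414 = 0.84. An observed difference of −1 gives −2.40 to 0.40 or −1.84 to −0.16.

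**HBeAg cells, treated as two arms.**

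| Cell | Control SD | Common SE | True SE | Excess |
|---|---|---|---|---|
| 4/12 | 0.6 | 1.12 | 0.69 | 61% |
| 6/18 | 0.4 | 0.90 | 0.53 | 68% |
| 3/9 | 0.4 | 1.29 | 0.76 | 71% |
| 7/21 | 0.4 | 0.83 | 0.50 | 68% |

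In these cells even the correct half-width exceeds 1 (1.02 at 7/21, more elsewhere), so an observed difference of 1 covers zero either way.

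**Repeated-measures check.** A simulated complete-data unstructured model over Weeks 1–24, 10/30, SDs 0.4 and 2.16, stratified allocation, gave a mean model SE of 0.69 against an SD of the estimates of 0.40–0.41. Repeated visits do not remove the problem.

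**Dependence on the SDs.** If the active SD were 0.8 (assumed) against 0.4, the common SE is sqrt(0.526 × 0.1333) = 0.26 and the true SE sqrt(0.0160 + 0.0213) = 0.19, an excess of 37%. At equal SDs there is none. The untreated model also contains the monotherapy arm, for which Table 7 gives no SD. If that were 2.16 (assumed), the common variance is (9×0.16 + 58×4.666)/67 = 4.06 and the SE 0.74 against 0.41.

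**Baseline log10 HBsAg.** The baseline-change correlation r is not in the documents, so r = 0.3 and 0.5 are assumed. Simulated with stratified allocation, 10/30, the ratios of true variance (adjusted over unadjusted) are:
- equal SDs, baseline-by-visit: 0.97 (r = 0.3) and 0.89 (r = 0.5), or SEs about 2% and 6% smaller;
- equal SDs, r = 0.5, baseline main effect only: 1.00 if the slope grows over visits, 0.87 if it is constant;
- SDs 0.4 and 2.16, baseline-by-visit with a slope common to the arms: 1.03–1.08, or SEs about 1–4% larger;
- SDs 0.4 and 2.16, arm-specific slopes: 0.95–0.99.

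Adjusted and unadjusted estimates centred on the same value.

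**The case against.** The study is exploratory with no formal testing, and an SE that is too large is conservative for this comparison. The protocol's primary-endpoint analysis is Bayesian (11.3.1); its sample code has a separate scale parameter for each arm, and the dose-response test takes one SE per dose group. Protocol 11.3.3 is headed as other analyses. All of this is true and limits the consequence. It does not remove it: 11.3.3 covers serologic parameters at every time point, and the SAP reports this model's CIs and p-values under the primary endpoint.

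The size rests on planning SDs. Protocol 1.1 reports no notable HBsAg change over 28 days in Phase 1, so the active-arm SD may prove well below 2.16 and the excess smaller. That stands as a condition on the size. The protocol's commitment does not depend on it.

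Separate covariance matrices are hard to estimate with ten controls: an unstructured matrix over eight visits has 36 parameters. This also stands, and it is why the fix needs a simpler structure and a fallback.

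A reader might infer that omitting baseline HBsAg and its stratum biases the treatment effect, or that adding them would narrow intervals substantially. The documents support neither. Under randomisation with complete data the unadjusted difference is unbiased. No r is given, and stratified allocation already captures part of any gain. At the Table 7 SDs the gain is about nil, and a common slope can do slight harm.

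**Conclusion.** The mismatch between Protocol 11.3.3 and SAP 5.2.1.1 with Appendix 3 is real. At the Table 7 SDs the SE for JNJ-56136379+NA versus placebo+NA is about 59–67% too large at 10/30, and about 60–70% too large in the HBeAg cells. This assumes complete data and two arms, and it shrinks to nothing as the arm SDs converge. The effect is on reported SEs, CIs and p-values of an exploratory model. It should not be read as invalidating the Bayesian primary analysis or the Table 7 power.

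Baseline adjustment is a minor, optional precision step: a few percent in the true SE if the arm SDs are similar and r is about 0.3–0.5 (assumed), and about nil at the planned SDs. That it is not a bias issue assumes complete data, or missingness that does not depend on baseline HBsAg given the observed changes.

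**What to change.** **Main change.** State in SAP 5.2.1.1 that residual covariance is estimated separately by treatment group, and add a treatment grouping option to the covariance statement in Appendix 3 and its fallbacks. Where an unstructured matrix per arm cannot be estimated, use a simpler one by arm; ARH(1) needs 9 parameters per arm over eight visits. If that does not converge, use a Week 24 comparison with arm-specific variances and Satterthwaite-type degrees of freedom. Fix this order in advance.

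**Optional.** In the HBeAg-pooled model only, add baseline log10 HBsAg, with baseline-by-visit if estimable. Do not require it in the small HBeAg-specific cells: at 3/9 it costs about 6% in SE if baseline is not prognostic, and breaks even only at |r| of about 0.33.

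**Cost.** A short change to the SAP text and code, with no new data. The drawbacks are some convergence risk and, with a simpler structure, an assumed correlation pattern. The full combination of baseline, baseline-by-visit and ARH(1) by arm has not been simulated, so no gain should be claimed for it. In the pooled models, baseline costs about 0.4–1.4% in SE if it is not prognostic (equal-SD calculation).

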### **5.2.1.2 Bayesian Efficacy Analysis**

For each of the comparisons listed above, a Bayesian approach will be employed. Non-informative priors will be used for the JNJ-56136379 arms. The prior for the mean of the placebo+NA treatment arms, on the other hand, will consist of a meta-analytic predictive (MAP) prior, derived from historical data. For the residual variance, a non-informative prior will be used for all treatments. To explore the robustness of the Bayesian analysis to a potential prior-data conflict, the analysis will be conducted with both full and no borrowing and the results compared.

A systematic review of published data on the HBsAg change from baseline at Week 24 in treatment of subject populations with NA (tenofovir, entecavir) has been carried out by Clinical Virology and Statistics & Decision Sciences. The respective MAP distributions for the different subject populations have been derived based on a pre-final version of this database. Since the MAP distributions are not of standard form, they are each approximated

---

as a mixture of normal distributions. The resulting normal mixtures, with corresponding component means and variances, are summarized in **Table 3**.

